# **DOUBLE-BLINDED, RANDOMIZED, CONTROLLED TRIAL TO STUDY THE EFFECT OF OMNILUX LIGHT-EMITTING DIODE ON WOUND HEALING FOLLOWING LOWER EXTREMITY SURGICAL WOUNDS LEFT TO HEAL BY SECOND INTENTION**

**Amendment #1: 12/10/12**

## **I. INTRODUCTION**

The first published data that the LED (Light Emitting Diode) light may be beneficial during wound healing occurred during the 18th century by Fubini and colleagues. Their early work on subcellular organelles was confirmed nearly 100 years later by Tina Karu demonstrating that 633 nm light targeted cytochrome c in the mitochondrial electron transport chain. Much recent research on LED has occurred largely as a result of NASA's program to develop a light source to grow plants on space shuttles. This recent research has focused on how the LED works on biological tissue and its applications to medicine.

Similar to the 633 nm light emitted by the LED, red light from the HeNe 633 nm laser has been shown to induce fibroblast monolayer formation faster with better alignment when compared to non-irradiated controls. The LED, when used in the 830 nm range, stimulates macrophages and neutrophils to perform chemotactic, phagocytic functions more quickly. It also increases fibroblast release of fibroblast growth factor by nearly 30 times. Perhaps most intriguingly, 633 nm and 830 nm LED light has been shown to stimulate keratinocytes to release a large amount of cytokines, and migrate into the dermis to aid in the dermal wound healing process. These photoactivated keratinocytes improve the cellularity and epidermal organization especially in the stratum corneum.

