of 4 treatments for both the experimental and control/sham groups. The wounds will be created as a result of Mohs micrographic surgery or surgical excision, and left to heal by secondary intention. An Aranz silhouette camera will be used with a measurement stick on the picture. Changes from the baseline wound (including length and width) will be measured along with wound depth. These two parameters will be compared at the 1 week, 2 week 3 week, and 4-week treatment (or sham treatment) visits. After the 4th and final treatment with the LED or sham light, the patients will be followed at 1-week intervals (+/- 3 days) until the wound has closed or for a maximum of 3 months, whichever occurs first. Once the wound has closed, patients will be evaluated a final time, 1 week after wound closure to ensure that complete wound healing has indeed occurred. After this final wound evaluation, the patient's commitment required for this study will end and regular follow-up with dermatology will resume outside the scope of this study.

The clinical photographs taken before and after either LED or sham light treatment at each study visit will be evaluated by blinded assessor(s) who are board-certified dermatologist(s).

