##### **B. Inclusion Criteria**

Surgical defect on the lower extremity left to heal by secondary intention. There is no minimum size for the wound. Women of child-bearing potential must be using medically-accepted contraceptive measures in order to participate in the study. Patients must be able to complete all study-related visits as scheduled. Maximum size of the wound is 5cm x 5cm.

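### Section III names length, width and depth but no open wound area, so partial closure that changes the wound's shape can be under-measured at weeks 1 to 4

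*Combined protocol and SAP*

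**What the plan says.** Section III is the only place that says how healing is measured. On the image it states: "An Aranz silhouette camera will be used with a measurement stick on the picture". On the measures: "Changes from the baseline wound (including length and width) will be measured along with wound depth". On the comparison: "These two parameters will be compared at the 1 week, 2 week 3 week, and 4-week treatment (or sham treatment) visits". Three dimensions have just been named, so the two parameters could be length and width, or planar change and depth.

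No section mentions wound area, tracing or percent area reduction. Section VII (Statistical Considerations) speaks only of wound size, which it does not define, and leaves the choice between ANCOVA and a t test open. The eligibility limit in Section IV.B is also given as two axes: "Maximum size of the wound is 5cm x 5cm".

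Section III has two further relevant provisions. Patients are followed weekly "until the wound has closed or for a maximum of 3 months, whichever occurs first", and then "patients will be evaluated a final time, 1 week after wound closure to ensure that complete wound healing has indeed occurred". Photographs from each visit are judged by blinded dermatologists, but no rating scale or area measure is given for them.

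**The concern.** A wound left to heal by second intention closes by losing open, non-epithelialised surface. Two axes follow that loss well only while the wound keeps its shape. If new epithelium forms an island inside the wound, or covers it unevenly, open area can fall while the outer length and width stay where they were. If the wound contracts in one direction only, the two axes give different answers, and the plan has no rule for which one represents healing. It also does not say whether the same line is measured at each visit.

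Part of the scientific rationale is epithelial. The Introduction says of the light's effect: "These photoactivated keratinocytes improve the cellularity and epidermal organization especially in the stratum corneum". Surface cover is the component that outer dimensions can miss. At stake is the sensitivity of the weeks 1 to 4 comparisons in a trial of 40 patients. So is the freedom, if the measure stays unnamed, to choose among length, width and their product after the results are seen.

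**Working it through.** The documents state no figure on this point and give no wound data, so there is nothing to reproduce. The check is geometry.

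**Inputs.** Largest eligible wound 5 x 5 cm (Section IV.B). The 3 x 2 cm and 40 x 20 mm wounds are illustrative sizes within that limit. Assumption: length and width run from outer margin to outer margin. The protocol does not say so.

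**1. Regular closure.** Ellipse area = (π/4) × L × W, so L × W overstates area by 4/π = 1.273, or 27%, at every visit. The factor is constant and cancels in percent change. If both axes shrink by 30%, L × W and area both fall by 1 - 0.7² = 51%. There is no distortion here.

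**2. Central island.** In a 5 cm circle, a healed island of diameter d removes (d/5)² of the open area:
- d = 1 cm: 4%
- d = 2 cm: 16%
- d = 3 cm: 36%

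Both axes change by 0% in each case.

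**3. Same axes, different outline.** With both axes fixed at 5 cm:
- circle: (π/4) × 25 = 19.6 cm²
- diamond: 25/2 = 12.5 cm², which is 36% less
- cross with 1 cm arms: 5 + 5 - 1 = 9 cm², which is 54% less

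**4. Axes that disagree.** From 3 x 2 cm to 3 x 1 cm, length changes by 0%, width by -50%, and elliptical area by 1 - 3/6 = 50%.

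**5. Shapes that need care.** Take a 40 x 20 mm ellipse, area (π/4) × 40 × 20 = 628 mm².
- *Crescent left by an internally touching patch.* The patch is a same-shaped ellipse with axes scaled by √0.5 (28.3 x 14.1 mm) that touches the edge from inside. Half the area is lost, and both outer dimensions are unchanged.
- *Crescent left by healing that advances from one side.* If the healed region is the same ellipse shifted along one axis and half the area remains open, the extent along that axis is (1 + 0.404)/2 = 70% of its starting value. That axis falls by about 30%, so the change is visible, though smaller than the 50% loss of area.
- *Transverse bridge.* A strip out to a fraction t of the half-length covers (2/π)(t√(1 - t²) + arcsin t) of the area and leaves a maximum width of 20√(1 - t²) mm. Half the area is t = 0.404, so width is 18.3 mm (-8.5%). The middle half of the length is t = 0.5, so 61% of the area is lost and width is 17.3 mm (-13%). Length stays at 40 mm only if it is measured across healed skin.

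**6. What this could cost in power (assumed inputs only).** Assume 20 per arm, two-sided alpha 0.05 and a true standardised difference of 0.886 in area change, which gives 80% power. If an axis-based score correlates ρ with area change and the effect shrinks in proportion:

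| ρ | Power | n per arm for 80% |
|---|---|---|
| 0.95 | 76% | 23 |
| 0.9 | 71% | 25 |
| 0.8 | 61% | 32 |
| 0.7 | 50% | 41 |

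No value of ρ is in the documents, so the table gives a range and does not estimate the loss in this trial.

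**The case against.** The strongest reply is that the plan has not committed to two axes. The list is introduced by *including*, so area is unspecified rather than excluded. Depth is measured too, and the two parameters may well be planar change and depth. Section VII refers to a single wound size, and no primary endpoint is fixed. For wounds that shrink evenly the choice makes no difference in percent terms, and nothing in the documents shows how often wounds heal otherwise. The camera's own outputs are not described.

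Most of this stands, and it limits the point. It does not remove it, because a measure that is not named is not prespecified, and the dermatologists' reading of photographs has no stated scale that could take its place. The fix needs only a picture with a scale in it, which Section III provides.

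Four stronger readings are tempting, and the documents do not support them.
- *Healing is scored from length and width alone.* The sentence is not exclusive, and it adds depth.
- *Real closure is missed.* Complete closure is followed weekly for up to 3 months and checked one week later. Only partial closure in the weekly comparisons is affected.
- *Any bridge or crescent leaves both axes unchanged.* Step 5 shows that a central bridge narrows the maximum width, and that healing from one side shortens one axis by about 30% when half the area is lost. The exact cases are a healed interior island and a crescent left by an internally touching patch.
- *The treatment is expected to act only on epithelium.* The Introduction also cites fibroblasts, macrophages and neutrophils, and has keratinocytes aiding dermal healing. Depth is relevant to those effects.

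**Conclusion.** The point holds for partial closure at weeks 1 to 4. The protocol names length, width and depth, but no open area and no rule for placing or combining the axes. In the worked shapes with both axes unchanged, open area falls by 4% to 54%. In the one-direction example one axis shows no change while the other halves. These sizes assume outer-margin measurement and a change of shape. Their frequency in this population is unknown, so the effect on the trial's result cannot be stated. Complete closure, and percent change in length times width for wounds that stay elliptical, are unaffected. This is a cheap improvement to the measurement plan, not an error that invalidates the trial.

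**What to change.** In Section III, define the planar measure at weeks 1 to 4 as the open (non-epithelialised) wound area traced on the scaled image by an assessor blinded to group. Sum separate open islands, and apply one written tracing rule at every visit. Enter a closed wound as zero area.

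In Section VII, compare the groups on change in area from the pre-treatment image, adjusted for baseline area. This is the ANCOVA option already mentioned there. Name the image that serves as baseline: Section III places the first session about one week after surgery, so a day 0 image and a week 1 image taken before treatment would both qualify.

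Keep depth as a separate measure, and report length and width descriptively. Replace the reference to two parameters with the named measures.

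The change needs a few sentences of protocol text and a tracing rule. The camera, images and visits stay the same. The downside is a few minutes of tracing per image.

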#### **IV. SUBJECT POPULATION**

##### **A. Number of Subjects**

We plan to prospectively enroll 40 patients in this study.

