#### **V. STUDY PROCEDURES**

Those patients who have a surgical defect on the lower extremity that will be left to heal by secondary intention and are willing to participate in the study will be consented and enrolled in the study.

The following information will be recorded in a prospective fashion: Patient's age, gender, race/ethnicity, type of skin cancer removed, clinical size of lesion (mm) and size of resulting defect following surgery. It will also be recorded to what group, treatment with LED and standard wound care versus sham light treatment and standard wound care with no LED. Clinical photos of the lesion will also be taken.

The experimental group will receive treatment with the light emitting diode (LED) for 20 minutes of exposure at an intensity of 105 mW/cm^2 for a total of 126 J/cm^2, over the wound site. The LED emits light at wavelengths of 633 nm and 830 nm at fluences of 126 and 66 J/cm^2. This study will only utilize the 633 nm wavelength. The control group will receive sham light treatment for 20 minutes duration and standard of care for second intention healing without the LED treatment. This includes maintenance of a clean and moist wound environment. Patients will keep the wound covered with an occlusive bandage and will perform daily dressing changes. Daily gentle cleansing with soap and water and the application of antibacterial ointment as needed for wound hydration will be the recommended standard of care for both treatment and control groups.

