## **VII. STATISTICAL CONSIDERATIONS**

This will depend on whether we want to measure a change between the experimental and control group at particular time intervals and between groups (ANCOVA) OR do we just want to measure the difference between the control and experimental groups at particular time periods (t test). If we just do a t test, then we will not be able to make intragroup comparisons, but it will be very easy to analyze, yet still determine if the experimental group accelerates wound healing in comparison to the control group. In addition, we should probably run an unpaired t test at baseline to make sure no statistically significant difference exists in wound

size between the experimental and control groups, otherwise it could confound our results one way or the other.

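### Wound depth is one of two compared parameters, but the plan sets no baseline, change score or adjustment for it, which costs precision with about 20 patients per arm

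*Combined protocol and SAP*

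**What the plan says.** Four places in the combined protocol and SAP bear on depth.

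- **Section III (Study Plan), what is measured:** "Changes from the baseline wound (including length and width) will be measured along with wound depth". Change from baseline is attached to length and width; depth is added beside them.
- **Section III, what is compared:** "These two parameters will be compared at the 1 week, 2 week 3 week, and 4-week treatment (or sham treatment) visits". Depth is therefore a compared parameter. The same section puts the first light session one week after the wound is made, within 3 days either way.
- **Section V (Study Procedures), what is recorded:** "clinical size of lesion (mm) and size of resulting defect following surgery". Depth is not named and size is not defined.
- **Section VII (Statistical Considerations), the analysis:** it leaves open a choice between an ANCOVA with no covariate named and a t test of "the difference between the control and experimental groups at particular time periods (t test". It says the t test would be easy but would not allow within-group comparisons. On baseline it says "we should probably run an unpaired t test at baseline to make sure no statistically significant difference exists in wound" size, and does not mention depth.

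The sample is set in Section IV.A: "We plan to prospectively enroll 40 patients in this study". Section IV.B limits wounds to 5 cm by 5 cm and sets no depth limit.

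**The concern.** Depth some weeks after surgery depends partly on how deep the defect was at the start. Defects here come from Mohs surgery or excision, with no depth limit at entry, so starting depth may differ between patients. Adjusting for length and width need not remove that variation, because a small wound can be deep and a large one shallow.

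If depth is compared at each visit by an unadjusted t test, which Section VII allows, two things follow. A chance difference in starting depth between arms carries into every later depth comparison, where it can look like an LED effect or hide one. And the part of the variance that starting depth explains stays in the error term, in a trial with little precision to spare.

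The week-1 visit is also miscast. Light starts at that visit, so a depth reading taken before the light cannot contain a treatment effect. Section III lists week 1 among the comparison visits, although that reading is better suited to serve as the baseline.

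**Working it through.** The documents give no alpha, power, target effect, SD or reason for 40 patients, so there is no stated figure to reproduce. What follows is illustrative.

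**Inputs from the documents.** 40 patients (Section IV.A) in two groups, in blocks of two (Section III), so n = 20 per arm.

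**Assumptions, not in the documents.** Two-sided alpha 0.05, 80% power, no dropout, equal variances, approximate normality, and correlation r between starting and later depth of 0.3 to 0.8. Effects are in SDs of depth.

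**Step 1. Standard error of the unadjusted contrast.** sqrt(2/20) = 0.316 SD.

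**Step 2. Detectable difference.** Solve the noncentral t for 80% power, with df 38 unadjusted and df 37 with one covariate. The required ratio of difference to standard error is about 2.88 in both cases. Unadjusted, this gives 0.909 SD. With ANCOVA the residual SD is multiplied by sqrt(1 − r²). For a change score the SD is multiplied by sqrt(2(1 − r)), so the detectable difference is 0.909 × sqrt(2(1 − r)).

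| r | Variance removed by ANCOVA, r² | Detectable, unadjusted | Detectable, ANCOVA | Detectable, change score | Power for 0.7 SD, ANCOVA |
|---|---|---|---|---|---|
| 0.3 | 9% | 0.91 | 0.87 | 1.08 | 62% |
| 0.5 | 25% | 0.91 | 0.79 | 0.91 | 70% |
| 0.7 | 49% | 0.91 | 0.65 | 0.70 | 86% |
| 0.8 | 64% | 0.91 | 0.55 | 0.57 | 95% |

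Unadjusted power for 0.7 SD is 58%. A change score is worse than the unadjusted comparison when r is below 0.5 and never better than ANCOVA over this range.

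**Step 3. Chance imbalance in starting depth.** Its SD is also 0.316 baseline SDs, so its 95% range is ±1.96 × 0.316 = ±0.62. The chance of an imbalance above 0.5 SD either way is about 11%. An imbalance of 0.5 SD shifts the unadjusted contrast by 0.5 × r, from 0.15 SD (r = 0.3) to 0.40 SD (r = 0.8).

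**Step 4. False-positive rate given that imbalance and no true effect** (normal approximation). The cut-off is 1.96 × 0.316 = 0.62, and the conditional SD is 0.316 × sqrt(1 − r²).

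- At r = 0.3 the conditional SD is 0.302. The upper tail beyond (0.62 − 0.15)/0.302 plus the lower tail beyond (0.62 + 0.15)/0.302 gives 6.5%.
- At r = 0.8 the conditional SD is 0.190. The upper tail beyond (0.62 − 0.40)/0.190 gives 12%.
- With an imbalance of one standard error (0.316) the conditional rate is 5.0% at r = 0.3 and 2.7% at r = 0.8, so it does not exceed 5%.

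Averaged over all randomizations the rate is 5%.

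**The case against.** **Is depth really to be compared as a raw level while size is compared as change?** A reader might infer this from Section III, but the documents do not say it. The bracket about length and width opens with a word that does not exclude depth, and the phrase that adds depth says it is measured, not how it is analysed. Size in Sections V and VII is undefined. Section VII does not fix change from baseline for size either, since its t test is not described as using change scores. The text supports only that the handling of baseline depth is unspecified.

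**Is the depth comparison biased by how deep the surgeon cut?** A reader might infer this too. Light given a week later cannot affect starting depth, so under sound randomization starting depth adds noise and chance imbalance, not systematic bias. A shift from chance imbalance is already inside the unadjusted standard error and must not be added to it.

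**Is there no usable depth baseline?** That would go too far. Depth is due at week 1, and a reading before the light would be a pre-treatment value. The gap is that the plan neither fixes that order nor gives the reading that role.

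**Is this only a symptom of the undecided analysis?** In part. An ANCOVA for both parameters, each with its own baseline, would settle it. But Section VII names no covariate, so choosing ANCOVA alone would not ensure that depth is adjusted for depth.

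**Is the size of the problem assumed?** Yes. At r = 0.3, power for 0.7 SD rises only from 58% to 62%. The calculation also uses normal theory with constant variance, which wounds that have closed, with depth 0, would strain at later visits.

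**Conclusion.** The point holds as a gap in specification with a cost in precision. Depth is a compared parameter for which the plan sets no baseline, change score or adjustment, and one of its two analysis options would ignore starting depth. The average type I error is not inflated, and no bias is shown.

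With 20 per arm, and r assumed to be 0.3 to 0.8, adjustment lowers the detectable difference from 0.91 SD to between 0.87 and 0.55 SD. That runs from minor to substantial, and the documents do not show where in the range this trial lies. The change should be made because it uses a reading the trial already plans to take.

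**What to change.** 1. In Section III, state that depth at the week-1 visit is read before the first light exposure, by the same method as at later visits, and that this reading is the depth baseline. Say which time point the baseline wound refers to for length and width. The only size record listed is the defect after surgery, so the two parameters may have different baselines.
2. In Section VII, compare depth between arms at weeks 2 to 4 by ANCOVA with week-1 depth as covariate, not by a change score or an unadjusted t test. A baseline significance test does not replace this.
3. In Section V, add wound depth to the recorded data.

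**Cost.** Wording and one degree of freedom. No visit or device is added, and Section III already has photographs taken before and after the light at each visit. Week-1 depth stops being an outcome comparison, which loses nothing because no treatment has been given before it.

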## **III. STUDY PLAN**

Patients will be recruited from patients at the University of Miami Miller School of Medicine Mohs/Laser Unit. On the day of surgery and wound defect creation (day 0), patients will be informed of the study, and given the option of participating. If he or she decides to participate, the patient will be randomized into one of two groups in blocks of two by coin flip. The patient will remain blinded to the outcome of randomization. The experimental group will receive treatment with the light emitting diode (LED) for one session lasting 20 minutes of exposure at an intensity of 105 mW/cm^2 for a total of 126 J/cm^2 over the wound site. The LED emits light at wavelengths of 633 nm and 830 nm at fluences of 126 and 66 J/cm^2. This study will only utilize the 633 nm wavelength. The control group will receive sham light treatment for 20 minutes with standard of care for second intention healing and no LED treatment. In this case, a sham light treatment refers to regular light (not LED) exposure for 20 minutes. The sham light comes from the same device as the treatment light (Omnilux machine) however, this light has no anticipated effects on wound healing and is used simply to reduce the amount of bias that sometimes complicates the results of these studies. There is no added risk or benefit for the patients in the control group exposed to the sham light.

On day 0 the patients will be informed of the study and randomized into one of two groups by coin flip to either the experimental or control group. The patients will be blinded to which group they have been randomized too. Group 1 is the control group, which will receive sham light treatment and standard of care for lower extremity wounds. Group 2 represents the experimental group, which will receive LED treatment plus standard of care. The experimental group will receive treatment with the light emitting diode (LED) at 633 nm at one session lasting 20 minutes of exposure at an intensity of 105 mW/cm^2 for a total of 126 J/cm^2 over the wound defect, one week after wound creation (+/- 3 days). The control group will receive no LED treatment, however they will be exposed to a sham light for the duration of 20 minutes as well as receive standard of care for their lower extremity wound. Treatment will occur at one-week intervals (+/- 3 days) for a total

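### Wound size and depth are compared only at the four treatment visits, so week 1 cannot show a healing effect, week 4 cannot show the response to the fourth session, and no named comparison follows the full course

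*Combined protocol and SAP*

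**What the plan says.** All of the timing is in Section III (Study Plan).

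- **Allocation:** "On day 0 the patients will be informed of the study and randomized into one of two groups by coin flip".
- **First session:** given "over the wound defect, one week after wound creation (+/- 3 days").
- **Repetition:** "Treatment will occur at one-week intervals (+/- 3 days) for a total" "of 4 treatments for both the experimental and control/sham groups".
- **Measurements:** "Changes from the baseline wound (including length and width) will be measured along with wound depth".
- **Named comparisons:** "These two parameters will be compared at the 1 week, 2 week 3 week, and 4-week treatment (or sham treatment) visits".
- **After the fourth session:** "the patients will be followed at 1-week intervals (+/- 3 days) until the wound has closed or for a maximum of 3 months, whichever occurs first". One further check follows a week after closure. No between-group comparison of size, depth, proportion closed or time to closure is attached to this period.
- **Photographs:** "The clinical photographs taken before and after either LED or sham light treatment at each study visit will be evaluated by blinded assessor(s"). No such order is given for the wound measurements.

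Section VII (Statistical Considerations) does not fill the gap. It leaves the choice between ANCOVA and a t test open and refers to time points only in general terms.

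**The concern.** The objective in Section II is to evaluate the efficacy of the LED in these wounds, and the Introduction gives long healing time as the reason for the trial. A comparison can show a healing effect only if the tissue has had time to respond to the light. Here the comparison days and the session days are the same days.

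Two things are at stake. A chance difference at week 1 sits in the list of outcome comparisons and could be reported as benefit, although light cannot yet have changed the size of the wound. The results that would answer the trial's question, namely wound size after the full course and time to closure, have no planned comparison. With Section VII undecided, a follow-up visit could be chosen after the data are seen.

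**Working it through.** **Step 1. Reproduce the schedule.** The inputs, all from Section III, are a first session at week 1, an interval of one week and four sessions. The session days are 7, 7 + 7 = 14, 14 + 7 = 21 and 21 + 7 = 28. These match the four treatment visits named for the comparisons. A start on day 0 would put the sessions at weeks 0, 1, 2 and 3 and leave no 4-week treatment visit, so that reading does not fit.

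**Step 2. Count sessions at each comparison under both possible orders.**

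| Visit (nominal day) | Sessions given, measured before light | Sessions given, measured after light | Sessions given on an earlier day (either order) |
|---|---|---|---|
| Week 1 (7) | 0 | 1 | 0 |
| Week 2 (14) | 1 | 2 | 1 |
| Week 3 (21) | 2 | 3 | 2 |
| Week 4 (28) | 3 | 4 | 3 |

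The second and third columns depend on an order that the plan does not state. The last column does not. If wounds are measured after light, the newest session ended only minutes earlier and cannot have changed wound dimensions through healing. At week 4, three sessions have had healing time: 3 × 126 = 378 of 4 × 126 = 504 J/cm², or 75% of the course.

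**Step 3. Count named comparisons after the course.** There are none. The first scheduled follow-up visit is nominally day 28 + 7 = 35. With the ±3-day window it falls 7 − 3 = 4 to 7 + 3 = 10 days after session four. It is the earliest visit with all four sessions given and healing time after the last.

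**Step 4. Illustrate the size of the loss.** Section IV.A gives 40 patients and no alpha, power, effect size or standard deviation, so the loss cannot be derived from the plan. The following inputs are assumptions: 20 per arm, a two-sided 5% test, the normal approximation, and an effect proportional to the number of sessions that have had time to act. Then

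power = Φ(d × √(20/2) − 1.960), with d in SD units.

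- Effect with 80% power in full: d = (1.960 + 0.842) × √(2/20) = 0.886.
- Three-quarters of it: 0.75 × 0.886 = 0.664, and Φ(0.664 × 3.162 − 1.960) = Φ(0.141) = 56%.
- Full effect of 0.6 SD: 48%, falling to 30% at 0.45 SD.
- Full effect of 1.2 SD: 97%, falling to 81% at 0.9 SD.

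If later sessions add less than earlier ones, the loss at week 4 is smaller. If the response lags, it is larger. The week-1 finding needs none of these assumptions.

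**The case against.** The strongest reply is that the plan does collect data after the course, through weekly follow-up to closure or 3 months, and that Section VII leaves the analysis times open, so nothing forbids a later comparison. The first part is right, and it is why the remedy is cheap. The second part does not help: a comparison that is merely not forbidden is not planned, and the only times named are the four treatment visits.

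A reader might infer more than the documents support.

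- **That the week-1 comparison precedes all treatment and week 4 follows only three delivered sessions.** This requires measurement before light. The plan does not say so, and photographs are taken both before and after. What stands is that no healing time has passed since the first session at week 1, or since the fourth at week 4.
- **That baseline is the day-0 wound, so change from baseline is distorted by an untreated week.** Section III does not date the baseline. Day 0 is plausible, because Section V records defect size after surgery, but it is an inference. Even so, the untreated week is common to both randomized arms: it adds noise, not bias.
- **That a fixed share of the effect is lost across the four visits.** Any such share needs linear accrual by session, and averaging needs equal weights over visits, which the plan does not propose.
- **That randomizing a week before the first session is a flaw.** Randomization on day 0 is valid and unbiased. Section IV.B sets no minimum wound size, so closure in the first week is possible, but the documents give no frequency and state no analysis population. The Introduction says that healing often takes months.

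One caution applies to the remedy. Follow-up stops at closure apart from one check, so a wound that closes early may have no visit a week after the fourth session. A size comparison restricted to attended visits would lose the fastest healers.

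**Conclusion.** The point holds for the comparison times. Whatever the order of measurement and light, one of the four named comparisons (week 1) cannot show a healing effect, the last (week 4) cannot show the response to the fourth session, and none falls after the complete course. This rests only on the schedule in Section III and on the fact that wounds do not change size by healing within minutes. The effect on power cannot be computed from the plan. The fall from 80% to about 56% is an illustration on the stated assumptions.

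The point does not extend to bias from day-0 randomization, to a claim that no post-course data are collected, or to any change in how treatment is given. The correction should be made before any outcome data are examined, because a comparison time chosen later would not be credible.

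**What to change.** Amend Sections III and VII as follows.

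1. State that the wound is measured before light at each treatment visit.
2. Use the week-1 pre-light measurement as the baseline or as the ANCOVA covariate, and drop week 1 as an efficacy comparison.
3. Make the existing first follow-up visit, one week after the fourth session, the main size comparison. Score wounds already closed as zero area, so that fast healers are kept.
4. Compare time to closure between groups over the existing follow-up, censored at 3 months, and state the date from which time is counted.
5. Keep weeks 2, 3 and 4 as supportive comparisons.

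The treatment schedule, the visits, eligibility and the timing of randomization stay as they are. The cost is protocol wording, wound size recorded with the same camera at the existing follow-up visit, and a main result read about one week later than week 4.
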